1.8	Lay Summary of the study (typically less than 5 lines).	Patients with an episode of late life depression will be randomized to Automatic self-transcending meditation (ASTM)plus Treatment as Usual (TAU) or TAU alone to assess changes in Heart Rate Variability (HRV, a measure of cardiovascular autonomic health, along with other secondary measures such as depression, anxiety and quality of life.

2. 2. Background, Methodology and Analysis

#	Question	Answer
2.1	Has the study undergone a formal scientific or peer review (i.e. CIHR, NSERC, NIH)? If yes, please attach the approval letter (or	

	relevant correspondence).	
2.2	Outline the study rationale including relevant background information and justification. Cite references where appropriate.	LATE LIFE DEPRESSION AND CARDIOVASCULAR AUTONOMIC FUNCTION: Major depressive disorder in the elderly (in those >60 years of age), also known as late life depression (LLD), is common, disabling and associated with a high mortality rate caused by suicide as well as cardiovascular events1 compelling appropriate treatment. Research shows that in a naturalistic setting response rate to at least one antidepressant trial of adequate dose and duration alone is around 30-40%2 thereby necessitating usage of additional interventions3. Such therapies include psychological therapies, and, recently, various forms of treatments loosely defined as mind-body therapies such as biofeedback, energy healing, meditation, guided imagery, and yoga4. Mind-body therapies are being increasingly embraced by patients as they have negligible side effects, are easy to administer and display beneficial effects on the quality of life as well as comorbid anxiety. There is increasing research on the mechanisms and benefits of such therapies, however, good quality trial data is scant. It is well established that antidepressants work by mostly modifying neurotransmitter levels in the brain5. On the other hand, some mind-body therapies target multiple organ systems and hence could offer neurobiological advantages as depression is now recognised as a multi-system disorder. This is particularly relevant to the LLD population where there is increased prevalence of comorbid cardiovascular disorders 3. Hence, some mind body therapies when offered in combination with antidepressants might have a beneficial effect on both depression and the cardiovascular system. One of the ways of assessing the cardiovascular system is through measurement of various autonomic parameters i.e. heart rate, blood pressure and heart rate variability. The most commonly reported is heart rate variability (HRV) which is a manifestation of the interplay of the central nervous system and the autonomic nervous system on a beat-by-beat basis6. One of

the ways of its estimation is by calculating the elapsed time between two consecutive waves, called R waves, on a person's electrocardiogram (ECG). A consistent finding has been that there is reduced HRV in people who have suffered a myocardial infarction (MI), and this phenomena is a predictor of subsequent cardiac arrhythmia and even death7. In addition, through previous work the PI has found that in LLD there are significant cardiovascular autonomic disturbances compared to age matched controls after controlling for various risk factors8. Other studies conducted in depression across the human life span have found similar results 9,10. Hence, if there is a mind-body treatment that specifically targets autonomic dysfunction and has a positive benefit on depressive symptoms, it would be valuable to assess. The investigators would like to investigate such a therapy which has been selected based on previous reports of beneficial effects but has not been evaluated in a randomised controlled trial of LLD patients. AUTOMATIC SELF TRANSCENDING MEDITATION (ASTM): ASTM is a class of meditation that helps quiet the mind and induces physiological and mental relaxation whilst the eyes are shut. It utilizes a specific sound value (mantra) to draw attention inward and permit the mind to experience a restful but alert state of consciousness11-13. Research suggests that ASTM is easier to learn and to teach in comparison to other meditation techniques including mindfulness 14. Studies of adult and elderly ASTM practitioners have documented reductions in depressive symptoms, as well as improvements in cardiovascular function among elderly with and without cardiovascular disease. A study of adults with CVD further demonstrated improvements in HRV 15-18. Research further suggests ASTM may be particularly well suited to elderly populations. In a randomized controlled trial of elderly retirement home residents which evaluated ASTM with two other meditative techniques and treatment as usual, ASTM produced significantly greater improvements in cognitive

function, cardiovascular function and quality of life than all other treatment conditions 19. A subsequent meta-analysis of all-cause mortality rates among hypertensive elderly who had participated in stress reduction interventions found that ASTM practitioners had a 30% lower cardiovascular mortality rate than four other meditative or relaxation interventions 20. The investigators are currently conducting a pilot study to explore the feasibility of ASTM on HRV measurement and depressive symptoms in patients with LLD in a secondary care background (UWO HSREB #103966). Preliminary results suggest that patients can be recruited, find improvement in depressive symptoms and tolerate the therapy, confirming feasibility of a larger study through this grant. We predict that ASTM augmentation is an effective intervention that ameliorates the autonomic disturbance associated with LLD. and possibly has beneficial effects on depressive symptoms as compared to a control treatment as usual (TAU) group. REFERENCES: 1. Steffens DC, Skoog I, Norton MC, et al: Prevalence of depression and its treatment in an elderly population: the Cache County study. Archives of general psychiatry 2000; 57:601-607 2. Trivedi MH, Rush AJ, Wisniewski SR, Nierenberg AA, Warden D, Ritz L, Norquist G, Howland RH, Lebowitz B, McGrath PJ, Shores-Wilson K, Biggs MM, Balasubramani GK, Fava M; STAR*D Study Team. Evaluation of outcomes with citalogram for depression using measurement-based care in STAR*D: implications for clinical practice. Am J Psychiatry. 2006 Jan; 163(1):28-40. 3. Alexopoulos GS. Depression in the elderly. Lancet. 2005 Jun 4-10;365(9475):1961-70 4. Purohit MP, Wells RE, Zafonte R, Davis RB, Yeh GY, Phillips RS. Neuropsychiatric symptoms and the use of mind-body therapies. J Clin Psychiatry. 2013 Jun;74(6):e520-6. 5. Stahl SM, Grady MM. Differences in mechanism of action between current and future antidepressants. J Clin Psychiatry. 2003;64 Suppl 13:13-7 6. Heart rate variability for risk

Prevention and Treatment of Cardiovascular Disease in Adolescents and Adults through the Transcendental Meditation((R)) Program: A Research Review Update. Current hypertension reviews 2012; 8:227-242 19. Alexander, C. N., Langer, E. J., Newman, R. I., Chandler, H. M., and Davies, J. L. (1989). Transcendental Meditation, mindfulness, and longevity: an experimental study with the elderly. Journal of Personality and Social Psychology, 57 (6): 950– 964 20. Schneider, R. H., Alexander, C. N., Staggers, F., Rainforth, M., Salerno, J. W., Hartz, A., et al. (2005). Long-term effects of stress reduction on mortality in persons =55 years of age with systemic hypertension. American Journal of Cardiology, 95 (9): 1060– 1064 is a class of meditation that quiets the mind and induces physiological and mental relaxation whilst the eyes are shut. It utilizes a specific sound value (mantra) to draw attention inward and permit the mind to experience a restful but alert state of consciousness (9-11). There are many systems of meditative practices which vary widely in their cognitive procedures, goals and subsequently on their specific psychophysiological outcomes. Based upon these differences, distinct classes of meditation have recently been identified (12, 13) MBCT belongs to the class of 'open monitoring' practices which are characterized by dispassionate, nonevaluative monitoring of ongoing thoughts, feelings, sensations and experiences. In contrast, the category of ASTM involves taking the attention to successively finer states of a thought until thought is transcended and the mind experiences 'pure awareness' itself', the screen of awareness without any object of awareness. [14]. Open monitoring involves voluntary sustained attention, while ASTM involves automatic moving from attention to mental silence. According to several is recognized as ASTM easier to learn and instruct than Open Monitoring techniques (12). It also requires shorter daily practice. These factors may make ASTM particularly useful in clinically depressed populations where motivation and

compliance with treatment are of concern. ASTM has been found to reduce stress and improve cardiovascular function in healthy adults (12), and to improve cardiovascular function, cognitive function and quality of life in elderly retirement home residents (13). However, its feasibility and effects on HRV in people with LLD has not been investigated in a randomised trial. Personal experiences of two self-paying LLD patients from the PI's clinical case load who recently completed ASTM training, as well as a study of retirement home residents (13) suggest that ASTM could be feasible, appropriately suited to their age, as well as effective in reducing their depression symptoms. STUDY JUSTIFICATION: We suspect that both ASTM would be a feasible intervention that can later be tested for its potential to ameliorate the autonomic disturbance, and possibly have beneficial effects on depressive symptoms, in LLD. If so, this technique could be offered as treatment choices in the future for patients with LLD. REFERENCES 1. Steffens DC, Skoog I, Norton MC, et al: Prevalence of depression and its treatment in an elderly population: the Cache County study. Archives of general psychiatry 2000; 57:601-607 2. [name] A, O'Brien JT, Tan MP, et al: A study of orthostatic hypotension, heart rate variability and baroreflex sensitivity in late-life depression. Journal of affective disorders 2011; 131:374-378 3. Gorman JM, Sloan RP: Heart rate variability in depressive and anxiety disorders. American heart journal 2000; 140:77-83 4. Kemp AH, Quintana DS, Felmingham KL, et al: Depression, comorbid anxiety disorders, and heart rate variability in physically healthy. unmedicated patients: implications for cardiovascular risk. PloS one 2012; 7:e30777 5. Kemp AH, Quintana DS, Gray MA, et al: Impact of depression and antidepressant treatment on heart rate variability: a review and meta-analysis. Biological psychiatry 2010; 67:1067-1074 6. Servant D, Logier R, Mouster Y, et al: [Heart rate variability. Applications in

treatment resistant mild to moderate major depressive disorder (MDD). Diagnosis of MDD will be confirmed through a structured clinical interview (Structured Clinical Interview for DSM Disorder (SCID)). Participants will be recruited from primary, secondary and tertiary care centres in London, Ontario, SCREENING AND INITIAL ASSESSMENTS: Potential participants will be screened as per inclusion and exclusion criteria by the PI at the Geriatric Mental Health Program (as written in another part of the protocol). Upon selection, the following scales will be administered: interview for comorbid medical conditions (Cumulative illness rating scale- Geriatrics, CIRS-G), a screening cognitive examination (Mini Mental State Examination (MMSE)), depression severity assessment (Hamilton Depression score (HAM-D 21 items), Clinical Global Impression (CGI), self rated Geriatric Depression Scale (GDS)), anxiety (Geriatric Anxiety Inventory (GAI)), side effects (Toronto Side Effects Scale, (TSES)), Quality of Life (QOL profile seniors version (QOLPS), physical activity assessment (Physical activity scale of the elderly, PASE questionnaire) RANDOMIZATION: Participants will be randomized to either ASTM+TAU or TAU equally (1:1) using computer generated randomisation numbers available at random.org. Concealment of randomisation will be ensured by independent staff performing randomisation using a third party web based provider (http://www.sealedenvelope.com/). Computerised randomization will occur from the Geriatric Mental Health Program outpatient unit in London Health Sciences, London, Ontario. A telephone number will be available for study concerns/queries. Pre-randomized information will be stored using unique deidentifiers and downloaded on a secure database. It will not be possible to blind participants to intervention status. Outcome assessors and investigators will be blinded to treatment. It will not be possible to blind participants or staff providing treatment to the

2.5	Indicate the inclusion criteria.	inclusion in the study if they are: 1. Of either gender, between the age range of 60-85 years. 2. Have an Axis 1 diagnosis of mild to moderate major depressive disorder or bipolar disorder with HAMD-21 score of 8 to 22. 3. Consuming single agent or combination antidepressant therapy at therapeutic doses for a minimum of four weeks. 4. Of good general physical health with no severe cardiovascular disease in the past 12 months, no past history of neurological disease or seizures or history of diabetic neuropathy. 5. Sufficient hearing to be able to follow verbal instructions and able to sit without physical discomfort for 45 minutes. 6. Willing and able to attend 4 initial ASTM training sessions and 75% of weekly follow up sessions.
2.6	Indicate the exclusion criteria.	Participants will be considered ineligible for participating in the study if they are: 1. Participating in other similar studies. 2. Other significant mental health diagnosis (including Dementia, Substance dependence, Post traumatic stress disorder, panic disorder, Obsessive compulsive disorder, dissociative disorder, neurocognitive disorder and Personality disorder) 3. High risk of suicide as elicited by clinical interview. 4. Psychotic episodes within the past 12 months. 5. Recent (within the past 6 months) head trauma that required emergency care 6. Currently practicing any type of formal meditation, mindfulness or breathing techniques. 7. patients with severe cardiovascular disease in the past 12 months (myocardial infarction, stroke or TIA) as well as history of neurological disease (including Parkinson's Disease) or seizures NOTE: We are aware that patients with depression in this age group (60-85 yrs of age) have usually a number of comorbidities including hypertension, diabetes mellitus and a history of cardiovascular as well as cerebrovascular events for which they receive appropriate medications including, but not limited to, beta blockers, calcium channel blockers and antiarrhythmics. Hence, realistically speaking it would be impossible to

		exclude patients who have a history of a cardiovascular disease and are on treatment with various cardiovascular drugs that could influence the autonomic variables that we are interested in. However, the investigators are confident that by the process of randomization to the two treatment arms (ASTM+TAU and TAU alone) we shall be able to control for these variables equally to both the study arms.
, ,	Document the usual standard of care at the trial site(s) for this population (including diagnostic testing, frequency of follow up visits).	The standard of care for patients with late life depression involves starting them on an appropriate antidepressant from various classes such as SSRIs, (fluoxetine, fluoxamine, paroxetine, citalopram, escitalopram, sertraline, paroxetine), or NaSSA (mirtazapine) or Bupropion. Patients are also prescribed additional anxiolytic medications like benzodiazepines and trazodone if deemed necessary. Participants will be initiated and maintained on appropriate dosages of such medications as part of standard of care. The psychiatrist and/or his multidisciplinary team members might offer supportive therapy as part of standard of care.
1 / X	Document the study procedures and any study specific testing that will be done.	Automatic self-transcending meditation treatment sessions will be conducted, details have been provided above. This is a minimally invasive treatments not routinely performed as part of standard and is done for research purposes only. Furthermore, three extra visits to the neurovascular research lab will be required as a part of this study. These involve HRV testing through ECG measurements, along with BP measurements.
2.9	Will any participant(s) be withdrawn from or denied usual therapy, or be subjected to other restrictions for any condition in order to participate in the study?	No
2.10	If YES has been selected in question 2.9 above, please explain.	
2.11	Describe the primary and secondary outcomes of this study and how they will be measured.	PRIMARY (HEART RATE VARIABILITY) OUTCOME MEASURES AT WEEK 0, 12 AND 24: Participants from both arms will be asked to report to room 402, Neurovascular Research Laboratory or the Laboratory for Brain

and Heart Health, Labatt Health Sciences Building, Western University Campus (Only participants in the ASTM arm will be asked to attend follow up assessments at 24 weeks). 1. Heart rate will be monitored using an electrocardiogram (ECG) with three adhesive leads situated on the chest. 2. Blood pressure will be measured using a small cuff placed on a finger (Finometer) or using a wrist cuff device (Colin Pilot). These continuous measures of blood pressure will be confirmed against values obtained periodically by an automated sphygmomanometer (Dinamap). 3. Electrocardiogram: A standard electrocardiogram will be collected via small surface electrodes on the chest to determine heart rate. 4. A bellows placed around the chest will provide information on respiratory excursions. The main outcome of interest, HRV, will be calculated by standard deviation of all R-R intervals (SDNN) on ECG, root-mean square of successive differences (RMSSD), and number of R-R intervals differing by >50 m sec from adjacent intervals (NN50) in time domain analysis. All of these tasks are validated and performed in this laboratory. A number of approved HSREB protocols are in place for the same. SECONDARY OUTCOME MEASURES (WEEKS 0, 4, 8, 12, and 24): Depression and comorbid anxiety symptoms will be assessed by a blinded rater on various scales at study visit days (week 0, 4, 8, 12 and 24 weeks) (Again, only participants in the ASTM arm will be asked to attend follow up assessments at 24 weeks). These scales are (Hamilton Depression score (HAM-D 21 items), Clinical Global Impression (CGI), self rated Geriatric Depression Scale (GDS)), anxiety (Geriatric Anxiety Inventory (GAI)), Antidepressant medication adherence threshold will be set at 80% of pills consumed; other consumed medications will also be recorded. In addition other outcome measures including scales Physical activity (PASE), adverse events (TSES) and quality of life (QOLPS) will be assessed at all study visits (week 0, 4, 8, 12 and

2.12		24 weeks). ADDITIONAL PROTOCOL CONDITIONS: Individual patients will be withdrawn from the study interventions if it appears that to continue would be deleterious for their mental health or safety. This can be determined by the patient, the treating clinician and/or the research team and will be supported by the use of the HAM-D 21 particularly if there is an increase in the score for question 18 "suicide", or an increase in total HAM-D score.
2.13	What is the total sample size?	96
2.14	Is the sample size justified in the sponsor or other study protocol?	No
2.15	If YES in question 2.14 above, indicate the protocol page number. If NO, provide sample size justification.	The design for this investigation is a split-plot partial hierarchical factorial design analysis of variance with 2 primary treatment conditions (ASTM+TAU vs TAU) tested at fixed time intervals. Because the ASTM treatment is to be conducted with groups of 4 participants, sampling will be done to form random groups of four participants each which will be randomly assigned to the ASTM or Control condition. That is, participants are nested in groups that are nested in Treatment condition. The primary focus is the interaction effect of treatment on heart rate variability at Weeks 0 and 12, with the long term benefits assessed at 24 weeks. On the assumption that this effect size is medium (Cohen's f = .25), calculations (using G*Power)23 indicate that a sample size of 80 (4 in each of 20 groups) yield power estimates of .99 for both the interaction and the main effect of time. The power estimate for relevant simple main effects of time for the ASTM treatment condition is .93 (.83 Bonferroni adjusted). Simple main effects of treatment at each level of time are not expected for early time periods, but could be at 24 weeks with a significant linear by linear interaction of time and treatment. This contrast is estimated to have a power of .72 assuming a medium effect, but the effect might well be stronger with the cumulative effects of time. All secondary variables measured at the five time points will be analyzed with a similar design (i.e., a 2x5 split plot factorial design

		analysis of variance with groups crossed with time but nested in Treatment condition). With the total sample size of 80 this yields power estimates of .999 for both Time, and the Treatment x Time interaction. It is intended to test a total of 96 participants to cover a conservative estimate of 20% loss to follow up.
2.16	Describe the method(s) for data analysis.	Please see section 2.15
2.17	Is an interim analysis planned?	No
	If YES to question 2.17 above, please describe.	
	DUDIIC!	Peer reviewed publication Presentation
2.20	If report to participants or other is selected above, please explain.	
2.21	Does this study include any use of deliberate deception or withholding of key information that may influence a participant's performance or response?	No
	If YES in question 2.21 above, describe this process and provide justification for the planned deception or partial disclosure. Also describe how and when the participants will be debriefed. Please include the debriefing letter of information and consent.	
2.23	Are biological specimens to be taken or analyzed for the purposes of this research protocol?	No
2.24	Are any biological specimens being taken for future genetic testing or other unspecified testing or studies?	No
	The subsequent use of tissue or biomaterials (except blood) originally collected for diagnostic purposes must be approved by the Department of Pathology Tissue Use Committee prior to submission to the HSREB and a copy of their approval appended to this form. If the Tissue Committee approval is not available at the time of submission to the HSREB, ethics approval will be withheld until a copy of Tissue Committee approval is received.	Not applicable

3. 3. Drugs and Natural Products

#	Question	Answer
	Does the study involve drugs or natural	
	products? If NO, please proceed to the	No
	Clinic Trials tab.	
	Is Drug 1 an investigational drug?	
	Drug 1 - Generic Name	
	Drug 1 - Brand Name	
	Drug 1 - Dose	
	Drug 1 - Frequency	
	Drug 1 - Route	
	Drug 1 - Duration	
	Is Drug 2 an investigational drug?	
-	Drug 2 - Generic Name	
	Drug 2 - Brand Name	
_	Drug 2 - Dose	
	Drug 2 - Frequency	
3.14	Dose 2 - Route	
	Drug 2 - Duration	
	Is Drug 3 an investigational drug?	
3.17	Drug 3 - Generic Name	
3.18	Drug 3 - Brand Name	
	Drug 3 - Dose	
3.20	Drug 3 - Frequency	
3.21	Drug 3 - Route	
3.22	Drug 3 - Duration	
3.23	Is Drug 4 an investigational drug?	
3.24	Drug 4 - Generic Name	
3.25	Drug 4 - Brand Name	
3.26	Drug 4 - Dose	
3.27	Drug 4 - Frequency	
3.28	Drug 4 - Route	
3.29	Drug 4 - Duration	
3.30	Is Drug 5 an investigational drug?	
3.31	Drug 5 - Generic Name	
3.32	Drug 5 - Brand Name	
3.33	Drug 5 - Dose	
3.34	Drug 5 - Frequency	
	Drug 5 - Route	
	Drug 5 - Duration	
	Is Drug 6 an investigational drug?	

3.38 Drug 6 -	Generic Name
3.39 Drug 6 -	Brand Name
3.40 Drug 6 -	Dose
3.41 Drug 6 -	Frequency
3.42 Drug 6 -	Route
3.43 Drug 6 -	Duration
3.44 Is Drug	7 an investigational drug?
3.45 Drug 7 -	Generic Name
3.46 Drug 7 -	Brand Name
3.47 Drug 7 -	Dose
3.48 Drug 7 -	Frequency
3.49 Drug 7 -	Route
3.50 Drug 7 -	Duration
3.51 Is Drug	8 an investigational drug?
3.52 Drug 8 -	Generic Name
3.53 Drug 8 -	Brand Name

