5.5	If a research participant is/or becomes pregnant, breastfeeds a child or fathers a child while in the study, does their participation in the study pose a possible risk to the fetus or child?	No
	If YES is selected in question 5.5 above, please discuss these risks and indicate what monitoring will be undertaken during the study and following the study conclusion?	
	If a research participant fathers a child while in the study, will access to the health records of the "pregnant" partner and/or her child be required and/or will the woman or child be monitored by this study during and/or after the pregnancy?	No

6. 6. Recruitment and Informed Consent

#	Question	Answer
in i	Describe the method(s) for recruiting participants.	Investigators will approach their own patients/students Investigators will receive referrals from other Healthcare providers Advertising (i.e. poster or email or web-based). Please submit a copy of all advertisements. Database of people who consented to future contact (please provide REB number or database name below)
6.2	If OTHER or DATABASE OF PEOPLE is selected in question 6.1 above, please specify here.	REB protocols #102574, #100749,
6.3	Will personal health information (PHI) be used to identify potential participants?	No
	If PHI will be used, please describe the screening and consent process regarding PHI.	
	How will potential participants be contacted? Please provide a copy of all telephone scripts and correspondence documents in the attachments tab.	In Person Other

h h	If OTHER is selected in question 6.5 above, please specify in this box.	A poster in various primary care offices will be used to recruit participants to our study. Posters shall be placed in various community centres and libraries as well. Please see attached poster.
6.7	Describe the process for obtaining informed consent. Please attach a copy of the Information Letter/Consent Form, Audio/Video Recording Consent Form, and the content of any telephone script and/or any other material that will be used in the informed consent process.	Please see attached Letter of information.
	Indicate if the research will involve any of the following:	Patients
	Will minors or persons not able to consent for themselves be included in the study?	No

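### Eligibility bars current meditation and current study participation but not earlier ASTM training, so lapsed trainees, including people who completed the investigators' own pilot, can be randomised, and practice in the TAU arm is not recorded

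*Combined protocol and SAP*

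**What the plan says.** Two exclusions in section 2.6 bear on earlier exposure, and both are in the present tense. Item 1 excludes those "Participating in other similar studies" and item 6 excludes those "Currently practicing any type of formal meditation, mindfulness or breathing techniques". Neither has a look-back period, although other items in the same list do: 12 months for psychotic episodes, 6 months for head trauma, 12 months for severe cardiovascular disease. The only inclusion criterion in section 2.5 that mentions the technique is item 6, "Willing and able to attend 4 initial ASTM training sessions and 75% of weekly follow up sessions", which concerns willingness and not prior exposure.

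The documents also point to people who already have the training. Section 2.2 says: "The investigators are currently conducting a pilot study to explore the feasibility of ASTM on HRV measurement and depressive symptoms in patients with LLD". Later in the same section it cites the "Personal experiences of two self-paying LLD patients from the PI's clinical case load who recently completed ASTM training". Under section 6.1, "Investigators will approach their own patients/students"; section 6.2 lists the recruitment databases as "REB protocols #102574, #100749".

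Section 2.4 gives a home-practice log to the ASTM arm. Its description of the TAU arm contains neither a log nor a request to refrain from meditating before week 12, and section 2.9 says that no restrictions are imposed for participation.

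**The concern.** The trial is meant to compare being taught ASTM with not having it. ASTM is a learned skill that can be practised at home, so someone taught before enrolment keeps access to it whatever the allocation. A lapsed trainee in TAU who takes it up again moves toward the ASTM arm. A lapsed trainee in the ASTM arm starts from a baseline that earlier exposure may already have affected.

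The primary contrast is the treatment-by-time interaction on HRV between weeks 0 and 12 (section 2.15). Resumed practice in TAU during that interval pulls the contrast toward zero. Because practice in TAU is not described as recorded, the analysis could neither detect this nor examine it.

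**Working it through.** **Step 1. Take a lapsed trainee through the criteria.** Consider a patient who completed the pilot, or paid for a course, and has since stopped.
- Exclusion 1: not met, because the earlier study is over.
- Exclusion 6: not met, because practice has stopped.
- Inclusion 6: met, if the patient is willing to attend.
- The remaining criteria concern age, diagnosis, HAMD-21 score, medication, health and hearing. None refers to earlier meditation training.

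The patient is eligible. A patient still in the pilot is barred by item 1, and a patient still practising is barred by item 6. Recruitment is expected to run for 76 weeks (section 2.4), so people in the pilot at the start may complete it while this trial is open.

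**Step 2. After randomisation.** Allocation is 1:1. In TAU, practice before week 12 is neither prohibited nor logged. The offer of ASTM to TAU participants comes after week 12 and does not affect the week 0-12 contrast.

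**Step 3. Size of the dilution.** Let c be the share of TAU participants who were trained earlier, resume, and obtain the full ASTM effect. The expected difference becomes (1 - c) times its undiluted value. With 48 per arm (section 2.4):
- 2 trained controls: c = 2/48 = 4%.
- 5 trained controls: c = 5/48 = 10%.

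The counts 2 and 5 are assumptions, since the documents give no number. Under 1:1 allocation they imply about 2 x 2 = 4 and 2 x 5 = 10 trained people among the 96 enrolled. The model is an upper bound for a given count, because it gives every such control the full effect of a supervised 12-week programme.

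**Step 4. Reproduce the planned power, then dilute it.** Section 2.15 gives f = 0.25, N = 80 and power .99 for the interaction. Assumed, because not stated: alpha 0.05, correlation between repeated measures rho = 0.5, m = 2 time points, and no clustering by groups of four. Power comes from the noncentral F distribution with lambda = f² x N x m / (1 - rho) and df = (m - 1) and (N - 2)(m - 1).
- Undiluted: lambda = 0.0625 x 80 x 2 / 0.5 = 20, df 1 and 78, power 0.993. This agrees with the stated .99.
- c = 5% (2 of 40 analysed controls): f = 0.2375, lambda = 18.05, power 0.987.
- c = 10% (4 of 40): f = 0.225, lambda = 16.2, power 0.978.
- c = 20%: f = 0.20, lambda = 12.8, power 0.942.
- c = 30%: f = 0.175, lambda = 9.8, power 0.871.

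Power falls below 0.90 only at a share between 20% and 30%. The starting value depends on rho: undiluted power is 0.950 at rho = 0.25 and 0.878 at rho = 0.

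**The case against.** The strongest reply is that harm needs a chain of events. The patient must have been trained, have stopped, still have HAMD-21 of 8 to 22 on antidepressants, agree to attend the course, be allocated to TAU, and resume within 12 weeks. Nothing shows that anyone meets all of these. The only trained patients counted outside the pilot are two, and the text does not say that either has stopped. The pilot's number is not among the listed recruitment databases, and recruitment also draws on other practices, referrals and posters. This stands as a limit on size. It does not close the gap, because the own-patient and referral routes remain open.

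A reader might infer that the control arm is contaminated. The documents do not support that. Stable carry-over sits largely in the week-0 value, so bias in TAU arises mainly if practice resumes. A reader might also infer an equal dilution in the ASTM arm. That is not shown either: prior training is balanced in expectation, and a lapsed trainee who takes the full course may still change. Nor can the point be extended to self-rated scales in general. Sections 2.4 and 2.11 call only the GDS self-rated, and section 2.11 assigns depression and anxiety assessment to a blinded rater.

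A lifetime bar could also exclude someone taught decades ago, in a trial described as naturalistic. How far back to look is partly a matter of preference, but the present rule admits even someone taught very recently. Finally, the case report form mentioned in section 7.19 is not shown, so whether it records meditation history cannot be determined.

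**Conclusion.** The gap in eligibility is real and follows from the text: the rules admit people who have already been given the intervention, provided they have stopped practising and are no longer in the pilot. The consequence is conditional. It can bias the HRV contrast toward no difference if trained controls resume before week 12, and it means that week 0 is not a pre-exposure value for trained participants in the ASTM arm.

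The size is unknown and probably small. On the upper-bound model, 4% to 10% of the difference is lost with 2 to 5 trained controls of 48. The planned power is not seriously threatened at those levels, given rho = 0.5 and no clustering, but the effect estimate would still be attenuated. This is an inexpensive improvement that is worth making, not a flaw that invalidates the design.

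**What to change.** - Extend exclusion 1 to current or previous participation in an ASTM study, naming HSREB #103966.
- Extend exclusion 6 to previous instruction in ASTM or Transcendental Meditation, keeping the bar on current practice of any formal technique.
- Add one screening question on earlier training and earlier study participation.
- Record any meditation practice in both arms through week 12. Changing the criteria alone would leave practice during follow-up unrecorded in TAU, including practice taken up by controls who were never trained.

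The cost is the loss of the few candidates already trained, and one brief extra item for TAU participants at existing visits. The sample size does not change.
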